5.2 Secondary outcome measures

Secondary outcomes include adherence rates (for VCDs, this is 70% of women wearing the VCDs as instructed by their clinicians. For PFMT, this is women reporting attendance to 70% of their individualised planned program appointments).

Other secondary outcomes include retention rate (achieve 80% at 6 months follow-up); rates of missing data; patient-reported success rates and adverse events of VCDs; use of self-funded VCDs; waiting times for physiotherapy, establishing reliable recruitment projection and refining our pre-defined progression criteria for a potential future RCT.

Table 1: proposed progression criteria for a future RCT

Proposed Progression criteria for an RCT	Red	Amber	Green
Participant recruitment	<60%	61 - 79%	≥80%
Participant Retention*	<60%	61 - 79%	≥80%
Adherence rates ▲	<50%	51 - 69%	≥70%

*number of participants completing the 6 month follow-up

▲number of women wearing the VCDs as instructed by their clinicians and for PFMT attending 3 out of the 5 appointments or 70% of their individualised planned program.

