Secondary	
1. To establish the facilitators and barriers for recruitment (and specifically randomisation) for women and healthcare providers for a definitive RCT.
	
A. Understanding of attitudes and preferences of women and HCPs regarding VCDs as a management option for SUI,
 
B. Identification of potential factors impacting on the trial participation (e.g. randomisation/ follow up and recruitment; uncertainty, preference and trust in HCPs and researchers) and decisional regret).
 
C: Ethical and pragmatic issues impacting on the pilot RCT conduct/management and the fidelity of intervention delivery and adherence.

	
2. To establish the relevant outcomes for a definitive randomised controlled trial (RCT) from women's and healthcare professionals (HCPs) perspectives.
	Identification of key outcomes that matter to women as well as clinically important outcomes for HCPs.
	
3. To establish a reliable sample size and recruitment projection for a definitive RCT, the adherence of participants to the proposed treatments, response rates to questionnaires, and loss to follow-up rate.
	
A. The participants' adherence rates: i) for VCDs: 70% of women wearing the VCDs as instructed by their clinicians and ii) for PFMT: attending 70% of their individualised planned program appointments);
 
B. The retention rate i.e. achieve 80% retention at 6 months follow-up);
 
C. The rates of missing data; patient-reported success rates and adverse events of VCDs; use of self-funded vs NHS prescribed VCDs; waiting times for physiotherapy,
 
The above will enable establishing reliable recruitment projection and refining our pre-defined progression criteria for a definitive RCT.

Embedded qualitative study	
The qualitative study embedded in the trial, informed by Theoretical Framework of Acceptability and INCLUDE Framework and the FEEL GOOD study stage 1 findings, aims to identify attitudes and preferences of women and healthcare professionals HCPs (Clinician, physiotherapist
	

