3.1 Interventions to be evaluated

The interventions being compared are: 1) Vaginal Continence Devices (VCDs) and supervised PFMT and 2) supervised PFMT-only. Women will be randomised 1:1 to receive VCDs plus supervised PFMT or supervised PFMT only.

There are different VCDs brands used in clinical practice and some of them can be obtained on NHS prescription (for example Contiform®, Contrelle®, Diveen®, Efemia®). The choice of VCDs will be according to the hospital's standard practice and as a shared decision by women and their HCPs. All types of VCD will be permitted in the study, provided they are CE marked. See section 3.2 for further information.

Both groups will be referred to the physiotherapist for supervised PFMT. An individualised PFMT plan will be designed as per the patient's goals and the standard practice in the collaborating hospital. They will have the option of face to face or telephone appointments as per standard of care in the collaborating hospital. See section 3.3 for further information.

Figure 1: study overview

ICIQ-FLUTS^R International Consultation on Incontinence Questionnaire - Female Lower Urinary Tract Symptoms long form; ICIQ-FLUTS^R-sex International Consultation on Incontinence Questionnaire – Female Sexual Matters; ICIQ-LUTSqol^R lower urinary tract symptom related quality of life; PGI-I patient global impression of improvement; PFMT pelvic floor muscle training; VCD vaginal continence device

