3.3 Pelvic Floor Muscle Training (PFMT)

PFMT is a programme of exercises designed to improve pelvic floor muscle strength, power, endurance, relaxation or a combination of these. It is the first line treatment for women with stress and mixed urinary incontinence as recommended in the NICE guidelines (NG123).

In order to create a training effect on the pelvic floor muscles, PFMT entails the consistent practice of repeated voluntary muscle contractions with adequate exercise progression. A PFMT program aims to improve muscle strength, volume, and structural support. It increases contraction endurance; improves resting tone; improves muscle recruitment through improved nerve function and muscle fibre properties; and improve cognitive awareness of body posture and the difference between a relaxed and an unrelaxed pelvic floor.

Furthermore, during physical activities that raise abdominal pressure and cause UI, a PFMT program teaches how to contract and relax the pelvic floor muscles to enhance coordination and functional use in obstructing the urethra.

The fundamental physiological principles must be followed in order to increase muscle strength and endurance: specificity (muscles must be trained with exercise or physical activity that as closely mimics the necessary functional movement as possible), overload (muscles must exert more effort than usual until exhaustion), maintenance (exercises must continue in the longer term), and reversibility (exercise benefits will reverse if they are not performed regularly).

As part of the training regimen, the NICE guidelines (NG123) recommend performing at least eight vaginal contractions, three times a day, for treatment of stress or mixed urinary incontinence. However, the number of muscle contractions required may vary depending on the patient's objectives and the findings at the time of vaginal examination. Typically, the individualised PFMT strategy calls for working the pelvic floor muscles till exhaustion and then increasing the frequency gradually.

Women in both groups of our study will be referred to the physiotherapist for supervised PFMT. An individualised PFMT plan will be designed as per the patient's goals and the standard practice in the collaborating hospital. They will have the option of face to face or telephone appointments as per standard of care in the collaborating hospital.

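### PFMT adherence has two cut-offs in the protocol: the Table 1 footnote accepts 3 of 5 appointments (60%), while section 5.2 and the trial summary require 70%

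*Protocol*

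**What the plan says.** The protocol defines PFMT adherence in three places.

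- Trial summary, secondary objective 3, outcome A: "attending 70% of their individualised planned program appointments".
- Section 5.2, opening text: "For PFMT, this is women reporting attendance to 70% of their individualised planned program appointments".
- Section 5.2, footnote to Table 1: "for PFMT attending 3 out of the 5 appointments or 70% of their individualised planned program".

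The first two give a single threshold. The third adds an alternative.

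For the device, section 5.2 says: "for VCDs, this is 70% of women wearing the VCDs as instructed by their clinicians". Table 1 then has one adherence row, with red below 50%, amber 51 to 69% and green at 70% or more. Its footnote covers both behaviours in one sentence: "number of women wearing the VCDs as instructed by their clinicians and for PFMT attending", followed by the PFMT rule.

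On the number of sessions, section 3.3 says only: "An individualised PFMT plan will be designed as per the patient's goals and the standard practice in the collaborating hospital". A five-appointment course is mentioned nowhere except in the Table 1 footnote. Section 3.1 says "Both groups will be referred to the physiotherapist for supervised PFMT", so PFMT adherence concerns all 74 women (section 4.1) and VCD adherence the 37 in one arm.

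**The concern.** Table 1 is where the adherence percentage is turned into a colour, and its footnote is more lenient than the outcome definition in the same section. A woman on a five-appointment plan who attends three is counted differently depending on which sentence is applied. The protocol gives no order of precedence.

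Adherence is one of three proposed progression criteria. Section 1.2 reports that surveyed clinicians were unsure whether women would keep to combined PFMT and VCD use, so this is a question the pilot is meant to answer. If the number of women attending exactly three of five is appreciable, the two definitions give different answers from the same attendance records.

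A smaller, related gap is that Table 1 gives one row to two rates with different denominators. It does not say what the row shows if the VCD rate falls in one band and the PFMT rate in another.

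**Working it through.** **Inputs from the protocol.** PFMT thresholds: 3 of 5, or 70% (Table 1 footnote); 70% only (section 5.2 text and trial summary). Bands: red below 50%, amber 51 to 69%, green 70% or more (Table 1). Women: 74 randomised, 37 per arm (section 4.1). The adherence criterion has no sample-size calculation of its own, so there is no stated figure to reproduce.

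**Step 1: the two rules on a five-appointment plan.**
- 3/5 = 60%, which is below 70%.
- 0.70 × 5 = 3.5, so the 70% rule needs 4 attendances (4/5 = 80%).
- The rules disagree for women attending exactly 3 of 5, and for no others on that plan.

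**Step 2: size in terms of counts.** Reading the 3-of-5 limb as applying to five-appointment plans, the difference in the adherent share is (women on such plans attending exactly 3) / 74. Each such woman moves the rate by 1/74 = 1.35 percentage points. Near the green boundary one woman is enough: 52/74 = 70.3% is green and 51/74 = 68.9% is amber.

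**Step 3: illustration over a range of attendance.** The protocol gives neither attendance rates nor the share of five-appointment plans, so these are assumptions: all women have five-session plans, and each session is attended independently with probability q. With X ~ Binomial(5, q), the adherent share is P(X ≥ 3) under the footnote and P(X ≥ 4) under the 70% rule.

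| q | 3 of 5 | 4 of 5 |
|---|---|---|
| 0.60 | 68.3% amber | 33.7% red |
| 0.65 | 76.5% green | 42.8% red |
| 0.70 | 83.7% green | 52.8% amber |
| 0.75 | 89.6% green | 63.3% amber |
| 0.80 | 94.2% green | 73.7% green |

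At q = 0.70 the gap is P(X = 3) = 10 × 0.7³ × 0.3² = 30.9 points. If only half the women had five-session plans it would be 0.5 × 30.9 = 15.4 points.

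**Step 4: relaxing independence.** Attendance probably clusters within women, which leaves fewer at exactly 3. Use a beta-binomial with mean m and within-woman correlation ρ, that is a = m(1/ρ − 1) and b = (1 − m)(1/ρ − 1). At m = 0.70:

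| ρ | 3 of 5 | 4 of 5 | Gap (points) |
|---|---|---|---|
| 0.2 | 76.5% green | 56.4% amber | 20 |
| 0.3 | 74.4% green | 58.1% amber | 16 |
| 0.5 | 71.9% green | 61.4% amber | 10 |

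The colours still differ, but the gap falls from 31 points to between 10 and 20. Clustering can also remove the colour difference: at m = 0.65 and ρ = 0.3 (a = 1.52, b = 0.82) the shares are 68.6% and 51.1%, both amber. At m = 0.80 both rules stay green at all three values of ρ.

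**The case against.** The kindest reading of the footnote is that 3 of 5 serves a standard five-session course and 70% serves any other plan. This does not remove the conflict. Sections 3.1 and 3.3 describe only individualised plans, and section 5.2 and the summary allow no exception. The reading would also set 60% for one plan length and 70% for the rest.

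Other objections stand and limit the point:

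- **Combined row.** A reader might infer a joint criterion, in which each woman must meet both the VCD and the PFMT test. Two independent rates of 70% would then give 0.7 × 0.7 = 49%, which is red. The documents do not support this as the natural reading. The summary lists the two components as separate items, section 5.2 defines each in turn, the row heading is in the plural ("adherence rates"), and a joint test cannot apply to the PFMT-only arm. What is unstated is how two different colours combine.
- **Three colours from one data set.** A reader might infer that the same data can come out green, amber or red. That requires mixing the VCD rate with the PFMT rate in constructed counts. The conflict between PFMT cut-offs yields two answers.
- **Non-response.** Adherence is self-reported, and 70% among responders with 20% non-response is 0.7 × 0.8 = 56% of all randomised if non-responders count as non-adherent. Handling of missing adherence data commonly belongs in the statistical analysis plan, which is a separate document not seen here, so this is not an error in the protocol. For the same reason it cannot be asserted that the choice of rule is open until the data are seen.
- **Decision weight.** Table 1 is labelled as proposed, refining the criteria is itself a study output, and the primary outcome is recruitment. Adherence does not settle progression alone.

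**Conclusion.** The contradiction stands. One threshold is stated in two incompatible ways within the protocol, and no other section resolves it. A statistical analysis plan could choose between the two rules, but the protocol text would still disagree with itself.

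The practical effect depends on two quantities that the protocol does not give: how many women have five-appointment plans, and how many of those attend exactly three. With all plans at five sessions and attendance around 0.65 to 0.75 under independence, the footnote gives green where the 70% rule gives amber or red. The 31-point gap at 0.70 is near the upper end, because fewer five-session plans and clustered attendance both shrink it. At about 0.80 or more the colour does not change. The recruitment outcome is unaffected.

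The single row for VCD and PFMT adherence is a lesser matter. The two rates are defined separately elsewhere, and only the rule for combining them is missing.

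**What to change.** 1. Use one woman-level PFMT cut-off in the trial summary, section 5.2 and the Table 1 footnote. The 70% rule is already the wording in two of the three places. The documents do not show which was intended, so if the sponsor keeps 3 of 5, the other two must be changed to match.
2. Split the adherence row of Table 1 in two: VCD adherence among women randomised to the VCD arm (37), and PFMT adherence among all randomised women (74).
3. State in advance how the adherence criterion is judged when the two rows have different colours. The choice of rule is the sponsor's.

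The cost is wording in three places of the protocol, with the statistical analysis plan aligned, and no new data. The downside is that if 70% is kept, the PFMT criterion becomes harder to meet than the current footnote allows, possibly materially so where five-session plans are common.

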6. DATA COLLECTION AND PROCESSING

6.1 Measuring outcomes

A baseline questionnaire will be completed prior to randomisation. Follow-up questionnaires will be sent at 3 and 6 months post-randomisation. Table 2 summarises the sources and timing of outcomes measures.

Table 2: Outcome measures

	Baseline	3-months	6-months
Clinical assessment	○		
ICIQ-FLUTS (International Consultation on Incontinence Questionnaire - Lower Urinary Tract Symptoms Questionnaire)	○	●	●
ICIQ-LUTSqol International Consultation on Incontinence Questionnaire - Lower Urinary Tract Symptoms Quality of Life Questionnaire	○	●	●
ICIQ-FLUTSsex International Consultation on Incontinence Questionnaire Female Sexual Matters Associated with Lower Urinary Tract Symptoms	○	●	●
PGI-I		●	●
Adverse events		●	●

○ At clinic appointment or by post/ email

● By post, email, text – according to participant's preference

6.2 Baseline

The baseline questionnaires will collect information about participants' age, parity, smoking status, previous treatment, severity of urinary incontinence and ethnicity. As described, the following questionnaires are also included in the Baseline-pack: ICIQ-FLUTS, ICIQ-LUTSqol, ICIQ-FLUTSsex.

6.3 Follow-up

Participants will receive their follow-up questionnaires and any reminders according to their preference (see section 4.9).

6.4 Data processing

Data collected by the local sites will be entered by Research Nurses. Staff in the Trial office will work closely with local Research Nurses to confirm the data are as complete and accurate as possible. Postal follow-up questionnaires will be sent from and returned to the Trial Office in Aberdeen, where data entry will be done.

7. SAFETY

The FEEL-GOOD study comprises Pelvic Floor Muscle Training and the use of Vaginal Continence Devices for the management of female SUI. Adverse effects may occur related to either of these interventions.

7.1 Standard Definitions

Term	Standard definition
Adverse Event (AE)	Any untoward medical event affecting a clinical trial participant.
Serious Adverse Event (SAE)	Where any AE: 
• results in death;• is life threatening (i.e. the subject was at risk of death at the time of the event; it does not refer to an event which hypothetically might have caused death if it were more severe);• requires hospitalisation or prolongation of existing hospitalisation;• results in persistent or significant disability or incapacity;• is a congenital anomaly or birth defect;• is otherwise considered medically significant by the investigator.

Adverse events are not:

- Continuous and persistent disease or symptom, present before the trial, which fails to improve; such as voiding dysfunction, urgency, urgency urinary incontinence, pain or dyspareunia.
- Signs or symptoms of the disease being studied; or
- Treatment failure: persistence or recurrence of urinary incontinence.

Hospitalisations for treatment planned prior to randomisation and hospitalisation for elective treatment of a pre-existing condition will not be considered as an AE. Complications occurring during such hospitalisation will only be considered AEs or SAEs if they are likely to be related to the interventions or research procedures.

7.2 Trial specific considerations

Planned hospital visits for conditions other than those associated with urinary incontinence and/ or its treatment will not be collected or reported. Further UI treatment will be recorded as a secondary outcome measure, but will not be reported as serious adverse events.

In this trial, AEs that are potentially related to the trial procedures and interventions (VCDs, PFMT) will be recorded (see definition of “related” in section 7.5 below). **All serious related AEs will be recorded as SAEs.** Any deaths (any cause) will also be recorded as SAEs. We will not capture unrelated SAEs.

Due to the reporting and collection of these events as primary and secondary outcome measures, the following do not need to be reported as AEs or SAEs:

- Urinary symptoms
- Sexual dysfunction

Furthermore, pre-existing conditions and any pre-planned hospitalisations (e.g. elective surgery) not associated with clinical deterioration will not be classed as Serious Adverse Events.

Trial specific expected adverse events

The FEEL-GOOD trial involves interventions to treat stress urinary incontinence which are well established in clinical practice. Expected adverse events arising from PFMT and VCD usage are:

- pelvic or abdominal pain/ discomfort,

- low back pain
- vaginal pain/ discomfort/ irritation
- vaginal discharge/ ulceration or Smell,
- abnormal vaginal bleeding,
- bleeding during removal of the device
- urinary or vaginal infections,
- urinary retention requiring a catheter in the bladder
- VCD falling out
- VCD entrapment in the vagina requiring removal in theatre

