5. OUTCOME MEASURES

5.1 Primary outcome measure

The primary outcome is the feasibility of participant recruitment within the time scale (i.e. achieving 80% of the target within 6 months); see table 1.

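### Section 7.2 exempts urinary symptoms and sexual dysfunction from SAE as well as AE reporting, which conflicts with its own rule on serious related events and with 7.1

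*Protocol*

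**What the plan says.** Section 7.2 of the protocol restricts safety recording to events potentially related to the trial procedures and interventions, and then states: "All serious related AEs will be recorded as SAEs". The next paragraph carves out two classes. It begins "Due to the reporting and collection of these events as primary and secondary outcome measures" and continues "the following do not need to be reported as AEs or SAEs". The two items are "Urinary symptoms" and "Sexual dysfunction", with no qualifier on either.

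Further down, the same section lists the expected adverse events of PFMT and VCD use. The list includes "urinary retention requiring a catheter in the bladder" and urinary or vaginal infections.

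Section 7.1 defines an adverse event broadly, as any untoward medical event in a participant, and then sets out what is not one. The first exclusion reads "Continuous and persistent disease or symptom, present before the trial, which fails to improve; such as voiding dysfunction, urgency" and goes on to name urgency incontinence, pain and dyspareunia. The other two are signs or symptoms of the disease under study, and treatment failure.

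On outcomes, section 5.1 says "The primary outcome is the feasibility of participant recruitment within the time scale". Section 5.2 lists adverse events of VCDs as a secondary outcome but names neither a urinary symptom score nor sexual function. Table 2 in section 6.1 does schedule ICIQ-FLUTS and ICIQ-FLUTSsex, at baseline, 3 months and 6 months.

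**The concern.** It is reasonable not to file an adverse event form for a symptom that a questionnaire already measures as an outcome. The difficulty is that the exemption goes further and covers SAEs. An SAE report exists so that someone promptly judges seriousness, causality and expectedness; a symptom score at 3 or 6 months does not do that.

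A site that learns of an admission for new voiding difficulty, judged related to the device, has one sentence in 7.2 telling it to record an SAE and another telling it that none is needed. Two sites could resolve this differently for identical patients. At stake are Sponsor and REC sight of a serious event, and the consistency of the adverse event record. That record feeds a named secondary outcome and, under section 10, a between-group relative risk.

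**Working it through.** The protocol gives no figure on this point, so nothing can be recomputed. The check is to put the rules side by side.

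**Inputs.** Definition and exclusions (7.1); SAE rule, exemption and expected list (7.2); duty to document (7.3); content of an SAE record (7.4); expectedness (7.5); reporting routes (7.6); outcomes (4.9, 5.1, 5.2, Table 2).

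**Step 1: apply each rule to the same event.** In the first four rows the event is taken to be serious and related to the intervention.

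| Event | AE under 7.1? | SAE rule in 7.2 | Exemption in 7.2 | Route in 7.6 if reported |
|---|---|---|---|---|
| New voiding dysfunction, not catheterised retention | Yes, by the general definition; not pre-existing | Record | Exempt as a urinary symptom | Unlisted, so unexpected: expedited to Sponsor, REC within 15 days |
| New dyspareunia | Yes, same reasoning | Record | Exempt as sexual dysfunction | As above, unless coded to the listed vaginal pain |
| Retention needing a catheter | Yes by the general definition; 7.1 does not name it | Record; also on the expected list | Ambiguous | Expected: regular progress reports, no individual REC report |
| Urinary infection | Yes by the general definition | Record; also on the expected list | Ambiguous | As above |
| Pre-existing urgency that persists | No | Not applicable | Exempt; no conflict | None |
| Persistent or recurrent incontinence | No | Not applicable | Exempt; no conflict | None |

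The first two rows are direct contradictions, the next two are ambiguities, and the last two show where 7.1 and 7.2 agree. Worsening of a pre-existing symptom is less clear than new onset. The natural reading of the 7.1 exclusion is an unchanged, continuing symptom, but a symptom that worsens has also failed to improve, and the text does not say which is meant.

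**Step 2: does another section settle the order?** No. Section 7.3 requires documentation of events that meet the 7.2 criteria, so it carries the exemption forward. Sections 7.4 and 7.6 speak of relevant events and add no test that would restore an exempted one. Section 7.5 judges expectedness against the 7.2 list, which omits new urgency, dyspareunia and voiding dysfunction short of catheterised retention. If serious and related, these would be unexpected events, the category that 7.6 sends to the Sponsor by expedited report and to the REC. The exemption, read literally, stops them before that route begins.

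**Step 3: does outcome collection replace the report?** Only in part. The SAE process in 7.4 collects event type, date, severity, causality, and any investigation or treatment. The protocol does not describe the ICIQ scores as recording seriousness or causality. Under 4.9, non-responders are reduced to a one-page questionnaire, whose content is not given, and then to a single question about their incontinence. Under 4.10 a woman may stop questionnaires and remain in follow-up.

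**Step 4: does the stated reason hold?** Not for the primary outcome, which is recruitment under 5.1. It holds for outcome measurement more generally, because Table 2 schedules both ICIQ instruments, although 5.2 does not name them.

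**The case against.** The strongest reply is that the exemption is a sensible design choice and that a careful site would read it narrowly. Catheterised retention and urinary infection are named as expected events; listing them would be pointless if they were swallowed by the generic phrase on urinary symptoms. Section 7.1 also removes signs and symptoms of the disease studied and treatment failure, so in an incontinence trial much of what the exemption covers was never an adverse event. Other capture exists as well: follow-up questionnaires ask about side effects (4.9), and about AEs and SAEs, hospital admissions and contacts with healthcare professionals (7.3).

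Most of this stands, and it rules out several stronger readings that a reader might infer:

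- That 7.1 itself counts new retention as an adverse event. It never mentions retention; that comes from the 7.2 list, and only where a catheter is needed. That new symptoms are adverse events follows from the general definition and the narrow wording of the exclusion, not from an explicit statement.
- That serious retention would miss REC review because of the exemption. As a listed, expected event, catheterised retention would not go to the REC individually under 7.6 on either reading.
- That urinary and sexual symptoms are not collected as outcomes. Table 2 collects them; only the word primary is plainly wrong.
- That device-related pain disappears from the record. Vaginal, pelvic and abdominal pain are on the expected list.
- That a definite share of events will be lost. The protocol supplies no rate from which to calculate one.

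The reply does not remove the conflict for serious, related, unlisted events. A questionnaire answer may bring an admission to light, but the site then returns to 7.2 to decide whether to file a report, and 7.2 points both ways.

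**Conclusion.** The point holds in a limited form. Section 7.2 extends its exemption to SAEs without confining it to non-serious events, against its own rule on serious related events and against the narrower exclusions in 7.1. The clear gap is the serious, related, new urinary or sexual event that is not on the expected list; on the natural reading of 7.1, worsening of an existing symptom belongs there too. For catheterised retention and urinary infection the text is ambiguous, and many sites would report them because they are listed.

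The size cannot be quantified from the protocol. The exemption applies to all 74 planned participants; its device-related part concerns the 37 allocated to VCDs. Serious events of this kind may be few or absent, and the questionnaire items make under-reporting possible rather than certain. The conclusion rests on a literal reading of the exemption, on the absence of any stated order of precedence, and on new symptoms falling within the general definition in 7.1. It warrants correction because it concerns the route by which serious unexpected events reach the Sponsor and the REC.

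**What to change.** Amend section 7.2 in four respects:

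1. Limit the exemption to non-serious urinary symptoms and non-serious sexual dysfunction that are captured by ICIQ-FLUTS or ICIQ-FLUTSsex.
2. State that any serious related event is still recorded as an SAE, whatever its symptom class, and that events on the 7.2 expected list, including catheterised retention and urinary infection, are still recorded as AEs.
3. Delete the word primary from the rationale.
4. Reconcile 7.1 with 7.2, so that both say the same about new and worsened symptoms.

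The cost is an amendment to the protocol wording, a line in site training and a few more SAE forms. Non-serious symptoms measured by the ICIQ instruments stay exempt, so the routine burden on sites barely changes.
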